### **6.6.2. Prohibited Medications and Procedures**

The following medications and measures are prohibited:

- The concomitant administration of potent CYP3A4 inhibitors and inducers and moderate CYP3A4 inducers (see [Appendix D](#)). Based on the low overall bioavailability of topical ketoconazole, there are no restrictions on topical ketoconazole.
- Any concomitant use of a selective FGFR inhibitor (other than pemigatinib).
- Investigational study drug for any indication.
- Use of any anticancer medications other than the study medications being tested in this Protocol.

## 7. DISCONTINUATION OF STUDY TREATMENT AND PARTICIPANT DISCONTINUATION/WITHDRAWAL

### 7.1. Discontinuation of Study Treatment

#### 7.1.1. Reasons for Discontinuation

Participants **must** be discontinued from study treatment for the following reasons. Please note that if a participant discontinues study treatment for reasons other than disease progression or withdraw of consent, the participant should be followed until disease progression is documented.

- The participant becomes pregnant.
- Consent is withdrawn.  
Note: Consent withdrawn means that the participant has explicitly indicated that they do not want to be followed any longer; in this case no further data, except data in public domain, may be solicited from or collected on the participant. Participants may choose to discontinue study treatment and remain in the study to be followed for progression and survival.
- Further participation would be injurious to the participant's health or well-being, in the investigator's medical judgment.
- Unacceptable toxicity as noted in Section 6.5.
- The study is terminated by the sponsor.
- The study is terminated by the local health authority, IRB, or IEC.
- Disease progression has been reported by central radiology review.
- Other antineoplastic treatment is initiated, not including palliative radiation.

A participant **may** be discontinued from study treatment if a participant is noncompliant with study procedures or study drug/treatment administration in the investigator's opinion, the sponsor should be consulted for instruction on handling the participant.

#### 7.1.2. Discontinuation Procedures

In the event that the decision is made to permanently discontinue the study treatment, the EOT visit should be conducted. Reasonable efforts should be made to have the participant return for a follow-up visit. These visits are described in [Table 3](#) and [Table 4](#). The last date of the last dose of study drug(s)/treatment and the reason for discontinuation of study treatment will be recorded in the eCRF.

#### If a participant is discontinued from study treatment:

- The study monitor or sponsor must be notified.
- The reason(s) for withdrawal must be documented in the participant's medical record and the primary reason for withdrawal must be included in the eCRF.
- The EOT visit should be performed.

- The date of the EOT visit should be recorded in the IRT.
- Participants must be followed for safety until the time of the follow-up visit or until study drug/treatment-related toxicities resolve, return to baseline, or are deemed irreversible, whichever is longest.

If the participant discontinues study treatment and actively withdraws consent for collection of follow-up data (safety follow-up or disease assessment), then no additional data collection should occur; however, participants will have the option of withdrawing consent for study treatment but continuing in the follow-up period of the study for safety/efficacy assessments and survival follow-up.

## **7.2. Participant Withdrawal From the Study**

A participant may withdraw from the study at any time at his/her own request, or may be withdrawn at any time at the discretion of the investigator for safety, behavioral, compliance, or administrative reasons.

If the participant withdraws consent for disclosure of future information, the sponsor may retain and continue to use any data collected before such a withdrawal of consent.

If a participant withdraws from the study, he/she may request destruction of any samples taken and not tested, and the investigator must document this in the site study records.

See [Table 3](#) and [Table 4](#) for data to be collected at the time of study discontinuation and follow-up and for any further evaluations that need to be completed.

## **7.3. Lost to Follow-Up**

A participant will be considered lost to follow-up if he/she repeatedly fails to return for scheduled visits and is unable to be contacted by the study site.

The following actions must be taken if a participant fails to return to the clinic for a required study visit:

- The site must attempt to contact the participant and reschedule the missed visit as soon as possible and counsel the participant on the importance of maintaining the assigned visit schedule and ascertain whether or not the participant wishes to and/or should continue in the study.
- Before a participant is deemed lost to follow-up, the investigator or designee must make every effort to regain contact with the participant (where possible, 3 telephone calls and, if necessary, a certified letter to the participant's last known mailing address or local equivalent methods). These contact attempts should be documented in the participant's medical record.
- Should the participant continue to be unreachable, he/she will be considered to have withdrawn from the study.

## **8. STUDY ASSESSMENTS AND PROCEDURES**

### **8.1. Administrative and General Procedures**

#### **8.1.1. Informed Consent Process**

- The investigator or his/her representative will explain the nature of the study to the participant or his/her legally authorized representative and answer all questions regarding the study.
  - Informed consent must be obtained before any study-related procedures are conducted, unless otherwise specified by the Protocol.
  - Informed consent must be obtained using the IRB/IEC-approved version in a language that is native and understandable to the participant. A template will be provided by the sponsor or its designee. The sponsor or its designee must review and acknowledge the site-specific changes to the ICF template. The ICF must include a statement that the sponsor or its designee and regulatory authorities have direct access to participant records.
  - The ICF must contain all required elements and describe the nature, scope, and possible consequences of the study in a form understandable to the study participant.
- Participants must be informed that their participation is voluntary. Participants or their legally authorized representative will be required to sign a statement of informed consent that meets the applicable requirements and regulations for the country(ies) in which the study is being conducted as well as the IRB/IEC or study center.
- The participant must be informed that his/her personal study-related data will be used by the sponsor in accordance with local data protection laws. The level of disclosure must also be explained to the participant.
- The participant must be informed that his/her medical records may be examined by Clinical Quality Assurance auditors or other authorized personnel appointed by the sponsor, by appropriate IRB/IEC members, and by inspectors from regulatory authorities.
- The medical record must include a statement that written informed consent was obtained before the participant was enrolled in the study and the date the written consent was obtained. The authorized person obtaining the informed consent must also sign the ICF.
- Participants must provide consent to the most current version of the ICF(s) during their participation in the study.
- A copy of the ICF(s) must be provided to the participant or the participant's legally authorized representative.

Participants who are rescreened are required to sign a new ICF.

### **8.1.2. Prescreening and Screening Procedures**

Prescreening is allowed in cases where the site may need to consult with the sponsor on the eligibility of a potential participant's genomic alteration. This is not required for all participants; it applies only to those whose genomic alterations need to be reviewed for eligibility. Screening is the interval between signing the study ICF (not the prescreening consent form) and the day the participant is enrolled in the study (Cycle 1 Day 1). Screening may not exceed 35 days.

Assessments that are required to demonstrate eligibility may be performed over the course of 1 or more days during the screening process.

Procedures conducted as part of the participant's routine clinical management (eg, blood count, imaging study) and obtained before signing of informed consent may be used for screening or baseline purposes provided the procedure meets the Protocol-defined criteria and has been performed in the timeframe of the study (ie, within 35 days of Cycle 1 Day 1). For participants who are enrolled in the study, information associated with eligibility requirements must be entered into the appropriate eCRF pages.

Results from the screening visit evaluations will be reviewed by the investigators to confirm eligibility before enrollment or the administration of study drug. Tests with results that fail eligibility requirements may be repeated once during screening if the investigator believes the results to be in error. For screening assessments that are repeated, the most recent available result before treatment begins will be used to determine eligibility. Treatment should start as soon as possible, but within 3 days after the date of enrollment.

See Sections [5.4](#) and [5.5](#) for information regarding screen failures and replacement of participants, respectively.

### **8.1.3. Interactive Response Technology Procedure**

Each participant will be identified in the study by a participant ID number, which is a combination of the site ID and participant number. Site staff should contact the IRT to obtain the participant ID number during prescreening (if applicable) and screening. Upon determining that the participant is eligible for study entry, the IRT will be contacted to obtain the treatment assignment. Additionally, the IRT will be contacted at each regular study visit to update the study drug supply. Additional details are provided in the IRT Manual.

### **8.1.4. Distribution of Reminder Cards**

Participants will be provided with a reminder card at each visit. The reminder card will indicate the date/time of the next visit and will have an area on which the date and time of the last dose taken and the time of their last meal before the visit should be recorded.

## **8.1.5. Demography and Medical History**

### **8.1.5.1. Demographics and General Medical History**

Demographic data and general medical history will be collected at screening by the investigator or qualified designee and will include year of birth/age, race, ethnicity, medical and surgical history, and current illnesses. Medical history will include relevant medical or surgical treatment within the last 10 years that are considered to be clinically significant by the investigator.

### **8.1.5.2. Disease Characteristics and Treatment History**

A disease-targeted medical and treatment history will be collected at screening. Details regarding the participant's malignancy under study, including date of diagnosis, initial and current cancer stage, tumor histology, and relevant disease characteristics, and prior treatments, including systemic treatments, radiation, and surgical procedures, will be recorded.

## **8.2. Efficacy Assessments**

### **8.2.1. Tumor Imaging**

Objective assessment of tumor status is required using appropriate disease-specific techniques, and a central radiologic facility will be used to determine responses and will be logged in to the eCRF. RECIST v1.1 ([Eisenhauer et al 2009](#)), and RANO for participants with primary brain tumors, will be used, and the recommended method for measuring and following tumor burden will be CT scan to include the thorax, abdomen, and pelvis; the neck can be included if needed. Alternative modalities (eg, MRI) may be substituted for a CT scan at the discretion of the investigator, provided that the same modality is used throughout the study and that the methodology is consistent with RECIST v1.1 or RANO.

The schedule for efficacy assessments will be at screening (this will be considered the baseline scan), every 9 weeks (every 3 cycles), and then at EOT (if applicable). Imaging should continue in 9-week intervals regardless of delays in cycle starts. For participants showing a response, a confirmatory scan may be performed a minimum of 4 weeks (per RECIST v1.1 and RANO) from the previous scan. For participants showing a progression based on local radiologic review, treatment should not be discontinued until progression of disease has been determined by the ICR, unless the principal investigator believes it is in the best interest of the participant to discontinue treatment before receiving confirmation.

For participants who discontinue treatment for reasons other than disease progression, every effort should be made to continue monitoring their disease status by radiographic imaging until 1) start of new anticancer therapy, 2) documented disease progression, 3) death, or 4) end of study, whichever occurs first.

[figure not shown]
### **8.2.2. ECOG Performance Status**

ECOG performance status (see [Table 14](#)) will be assessed at the visits specified in the appropriate SoA (see [Table 3](#) and [Table 4](#)).

**Table 14: ECOG Performance Status**

Grade	Performance Status
0	Fully active, able to carry on all predisease performance without restriction.
1	Restricted in physically strenuous activity but ambulatory and able to carry out work of a light or sedentary nature, eg, light house work, office work.
2	Ambulatory and capable of all self-care but unable to carry out any work activities. Up and about more than 50% of waking hours.
3	Capable of only limited self-care, confined to bed or chair more than 50% of waking hours.
4	Completely disabled. Cannot carry on any self-care. Totally confined to bed or chair.
5	Dead.

Source: [Oken et al 1982](#).

## 8.3. Safety Assessments

See Section [6.5](#) for guidelines regarding the management of relevant laboratory or other safety assessment abnormalities.

### 8.3.1. Adverse Events

Adverse events will be monitored from the time the participant signs the ICF until at least 30 to 35 days after the last dose of study drug or until the start of new anticancer therapy, whichever occurs first. Adverse events that begin or worsen after informed consent should be recorded on the Adverse Events Form in the eCRF regardless of the assumption of a causal relationship with the study drug. Conditions that were already present at the time of informed consent should be recorded on the Medical History Form in the eCRF. Adverse events (including laboratory abnormalities that constitute AEs) should be described using a diagnosis whenever possible rather than by individual underlying signs and symptoms.

Adverse events will be reported by the participant (or, when appropriate, by a caregiver, surrogate, or the participant's legally authorized representative). The investigator and any qualified designees are responsible for detecting, documenting, and recording events that meet the definition of an AE or SAE and remain responsible for following-up on AEs that are serious, considered related to the study treatment/procedures, or that caused the participant to discontinue study drug. Care will be taken not to introduce bias when detecting AEs and/or SAEs.

Open-ended and nonleading verbal questioning of the participant, such as "How are you feeling?" is the preferred method to inquire about AE occurrences. Adverse events may also be detected when they are volunteered by the participant during the screening process or between visits, or through physical examinations, laboratory tests, or other assessments. The definition, reporting, and recording requirements for AEs are described in Section [9](#).

All SAEs will be recorded and reported to the sponsor or designee within 24 hours. The investigator will submit any updated SAE data to the sponsor within 24 hours of it being available.

After the initial AE/SAE report, the investigator is required to proactively follow each participant at subsequent visits/contacts. All SAEs will be followed until resolution, stabilization, the event is otherwise explained, or the participant is lost to follow-up (as defined in Section 7.3).

For Japanese participants only, the relationship of the adverse event to phosphate binder(s) should also be collected on the Adverse Events Form in the eCRF.

### **8.3.2. Physical Examinations**

Physical examinations must be performed by a medically qualified individual, such as a licensed physician, physician's assistant, or an advanced registered nurse practitioner, as local law permits. Abnormalities identified after the first dose of study treatment constitute an AE if they are considered clinically meaningful, induce clinical signs or symptoms, require concomitant therapy, or require changes in study drug. Investigators should pay special attention to clinical signs related to previous serious illnesses.

At the screening visit, a comprehensive physical examination should be conducted. The comprehensive physical examination will include height (at screening only) and body weight and assessment(s) of the following organ or body systems: skin; head, eyes, ears, nose, and throat; thyroid; lungs; cardiovascular system; abdomen (liver, spleen); extremities; and lymph nodes; as well as a brief neurological examination.

During the study, participants will be assessed by the investigator or medically qualified designee per institutional standard of care. These assessments should be an evaluation as indicated by participant symptoms, AEs, or other findings and documented on the AE eCRF.

### **8.3.3. Vital Signs**

Vital sign measurements (to be taken before blood collection for laboratory tests), include blood pressure, pulse, respiratory rate, and body temperature. Blood pressure and pulse will be taken with the participant in the recumbent, semirecumbent, or sitting position after approximately 5 minutes of rest. Weight will also be assessed at the beginning of each cycle. Abnormal vital sign results identified after the first dose of study treatment constitute an AE if they are considered clinically meaningful, induce clinical signs or symptoms, require concomitant therapy, or require changes in study drug.

### **8.3.4. Electrocardiograms**

Single 12-lead ECG will be obtained as outlined in the SoA (see Table 3) using an ECG machine that automatically calculates the heart rate and measures PR, QRS, QT, and QTc intervals. All 12-lead ECGs will be performed with the participant in a recumbent or semirecumbent position after approximately 5 minutes of rest.

The 12-lead ECGs will be interpreted by the investigator at the site to be used for immediate participant management. Additional 12-lead ECGs may be performed as clinically indicated to manage participant safety. The decision to include or exclude a participant or withdraw a participant from the study treatment based on an ECG flagged as "Abnormal, Clinically

"Significant" is the responsibility of the investigator, in consultation with the sponsor's medical monitor, as appropriate. Clinically notable abnormalities that are considered clinically significant in the judgment of the investigator are to be reported as AEs. In the event that a single QTc is > 480 ms at screening, the participant may enroll if the average QTc for the 3 ECGs is  $\leq$  480 ms or with approval from the medical monitor. For participants with an intraventricular conduction delay (QRS interval > 120 ms) at screening, the JTc interval may be used in place of the QTc with medical monitor approval. The JTc must be  $\leq$  340 ms if JTc is used in place of the QTc. In addition, the JTc interval should be used for all subsequent assessments.

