## 5. STUDY POPULATION

Deviations from eligibility criteria are not allowed because they can potentially jeopardize the scientific integrity of the study, regulatory acceptability, and/or participant safety. Therefore, adherence to the criteria as specified in the Protocol is essential. Prospective approval of Protocol deviations to recruitment and enrollment criteria, also known as Protocol waivers or exemptions, are not permitted.

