**Table 10: Exclusionary Laboratory Values**

Laboratory Parameter		Exclusion Criterion
Hematology		
a	Platelets	$\leq 75 \times 10^9/L$ (transfusion allowed with a 2-week washout period)
b	Hemoglobin	$\leq 9.0 \text{ g/dL}$ (transfusion allowed with a 2-week washout period)
c	ANC	$\leq 1.5 \times 10^9/L$
Hepatic		
e	ALT	$\geq 3 \times \text{ULN}$ ( $> 5 \times \text{ULN}$ for liver metastasis)
f	AST	$\geq 3 \times \text{ULN}$ ( $> 5 \times \text{ULN}$ for liver metastasis)
g	Total bilirubin	$\geq 1.5 \times \text{ULN}$ ( $\geq 2.5 \times \text{ULN}$ if Gilbert's syndrome or liver metastasis)
h	Alkaline phosphatase	$\geq 3 \times \text{ULN}$
Renal		
i	Serum creatinine clearance	$\leq 30 \text{ mL/minute}$ based on Cockcroft-Gault formula.
Chemistry		
j	Serum phosphate	$> \text{ULN}$
k	Serum calcium	Outside of normal range or serum albumin-corrected calcium outside of the normal range when serum albumin is outside of the normal range.

10. History of calcium and phosphate hemostasis disorder or systemic mineral imbalance with ectopic calcification of soft tissues (exception: commonly observed calcifications in soft tissues such as the skin, kidney tendon, or vessels due to injury, disease, or aging in the absence of systemic mineral imbalance).
11. Significant gastrointestinal disorder(s) that could interfere with absorption, metabolism, or excretion of pemigatinib.
12. Inability to swallow and retain oral medication.
13. Clinically significant or uncontrolled cardiac disease, including unstable angina, acute myocardial infarction within 6 months from Day 1 of study drug/treatment administration, New York Heart Association Class III or IV congestive heart failure, and uncontrolled arrhythmia (participants with pacemaker or with atrial fibrillation and well-controlled heart rate are allowed).
14. History or presence of an abnormal ECG that, in the investigator's opinion, is clinically meaningful. A screening QTcF interval  $> 480 \text{ ms}$  is excluded. For participants with an intraventricular conduction delay (QRS interval  $> 120 \text{ ms}$ ), the JTc interval may be used in place of the QTc with medical monitor approval. The JTc must be  $\leq 340 \text{ ms}$  if JTc is used in place of the QTc.

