8.5. Electrocardiograms

Twelve-lead ECGs including the heart rates and PR, QT, QRS, and QTc intervals will be obtained for each participant during the study. Values at each scheduled visit, change, and percentage change from baseline will be summarized for each ECG parameter. Baseline will be determined as the average of all nonmissing values before the first administration of pemigatinib.

Normal ranges for ECG values are defined in [Table 6](#). ECG values will also be considered abnormal if the absolute percentage change from baseline is more than 25% (QRS 30%). Participant exhibiting ECG abnormalities will be listed with study visit and assigned cohort. Abnormal values for participant with alert ECG values, defined as both the absolute value and the percentage change from baseline being outside normal ranges, will be identified and listed. Outliers of QT, and QTc values, defined as absolute values > 450 ms, > 500 ms, or change from baseline > 30 ms, will be summarized.

Table 6: Criteria for Clinically Notable Electrocardiogram Abnormalities

Parameter	High Threshold	Low Threshold
HR	> 100 bpm	< 45 bpm
PR	> 220 ms	< 75 ms
QT	> 500 ms	< 300 ms
QRS	> 120 ms	< 50 ms
QTc	> 460 ms	< 295 ms

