3.5 ECG		
3.5.1	Summary of PR Interval (ms) From 12-Lead ECG	Safety
3.5.2	Summary of QRS Interval (ms) From 12-Lead ECG	Safety
3.5.3	Summary of QT Interval (ms) From 12-Lead ECG	Safety
3.5.4	Summary of QTc Interval (ms) From 12-Lead ECG	Safety
3.5.5	Summary of Heart Rate (bpm) From 12-Lead ECG	Safety
3.5.6	Summary of Outliers of QT, QTcB, and QTcF Interval Values (ms) From 12-Lead ECG	Safety
3.5.7	Summary of Clinically Significant ECG Abnormality	Safety

Figures

Figure No.	Title
4.1.1	Kaplan-Meier Estimates of Progression -Free Survival
4.2.1	Kaplan-Meier Estimates of Duration of Response
4.2.2	Kaplan-Meier Estimates of Overall Response
4.3.1	Waterfall Plot of Best Percentage Change in Sum of Target Lesions
4.3.2	Swimmer Plot of Duration of Treatment
4.6.1	Line Graph of Selected Laboratory Values by Study Visit

Listings

Listing No.	Title

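### The > 450 ms QT/QTc outlier count in SAP 8.5 ignores baseline, so it cannot separate values already high at entry from newly occurring ones

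*Protocol*

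**What the plan says.** **Entry.** In Protocol Section 5.2, criterion 14, "A screening QTcF interval" above 480 ms is excluded. A QTcF of 451 to 480 ms is therefore eligible without any approval. Protocol 8.3.4 adds that where "a single QTc is > 480 ms at screening, the participant may enroll if the average QTc for the 3 ECGs" is at most 480 ms. The full limit in that sentence reads "480 ms or with approval from the medical monitor", and the approval route has no stated ceiling. Section 5 says that prospective approvals of departures from the entry criteria, "also known as Protocol waivers or exemptions, are not permitted".

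**Analysis.** SAP 8.5 has QT and QTc outliers "defined as absolute values > 450 ms, > 500 ms, or change from baseline > 30 ms, will be summarized". The display is Table 3.5.6 in SAP Appendix A, "Summary of Outliers of QT, QTcB, and QTcF Interval Values (ms) From 12-Lead ECG". Neither place limits the absolute categories to post-baseline ECGs, or to participants at or below the limit at baseline. The SAP does define an ECG baseline: "Baseline will be determined as the average of all nonmissing values before the first administration of pemigatinib".

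**Other ECG outputs.** SAP 8.5 also summarizes values and changes from baseline by visit. It lists alert values, which need both an out-of-range absolute value and an out-of-range percentage change (25% for QT and QTc).

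**Laboratory data, for contrast.** SAP 8.3.2 plans shift tables from baseline grade to worst post-baseline grade. Appendix A adds treatment-emergent worsening tables (3.3.3.4 to 3.3.3.6). The ECG tables, 3.5.1 to 3.5.7, include no shift table.

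**The concern.** The entry limit (480 ms) lies above the first outlier limit (450 ms). Anyone who enters in the 30 ms between them satisfies the > 450 ms category before taking any drug, and goes on satisfying it if nothing changes. A count built that way mixes two things: how many participants had a long QTc at entry, and how many developed one on treatment.

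ECGs are part of the safety secondary endpoint. The trial is single-arm, so no concurrent rate shows how large the first component is. The participant's own baseline is the only available reference, and this count does not use it. What is at stake is the reading of one descriptive safety table. No hypothesis test and no efficacy result is touched.

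**Working it through.** The plan states no figure for this quantity, so there is nothing of its own to reproduce. The check has three steps.

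**Step 1. Apply the SAP 8.5 rules to participants whose QTc does not change.** Inputs: outlier limits of 450 and 500 ms and the > 30 ms change (SAP 8.5); the QTc limit of 460 ms (SAP Table 6); the 25% change in the alert rule (SAP 8.5).

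| Constant QTc (ms) | > 450 | > 500 | Change > 30 | Above Table 6 limit | Alert | Newly > 450 |
|---|---|---|---|---|---|---|
| 445 | no | no | no | no | no | no |
| 451 | yes | no | no | no | no | no |
| 465 | yes | no | no | yes | no | no |
| 480 | yes | no | no | yes | no | no |

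Every stable value from 451 to 480 ms is counted as > 450 ms. None meets > 500 ms, the change category or the alert rule. A newly-occurring condition (baseline at or below 450 ms, worst post-baseline above it) removes all of them.

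The alert rule cannot sort the > 450 ms cases either. From a baseline of 425 ms, a 25% rise means passing 425 × 1.25 = 531 ms.

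**Step 2. How many entrants could lie between 450 and 480 ms?** The documents give no QTc distribution, so the mean (410 to 430 ms) and SD (15 to 25 ms) are assumptions. With a normal distribution cut at the 480 ms entry limit,

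share = [Φ((480 − μ)/σ) − Φ((450 − μ)/σ)] / Φ((480 − μ)/σ).

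- μ = 410, σ = 15: the share is about 1 − Φ(2.667) = 0.004; 170 × 0.0038 = 0.7.
- μ = 420, σ = 20: (0.9987 − 0.9332)/0.9987 = 0.066; 170 × 0.0655 = 11.1.
- μ = 430, σ = 25: (0.9772 − 0.7881)/0.9772 = 0.194; 170 × 0.1935 = 32.9.

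The 170 is the planned total enrollment (Protocol Table 2).

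**Step 3. What would each counting rule report with no drug effect?** Simulation of 200,000 participants per setting. Further assumptions: within-person SD 8 ms (part of the total SD), two pre-dose ECGs averaged as baseline, the first of them at or below 480 ms for entry, and eight on-treatment ECGs.

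| Mean, SD (ms) | Baseline 450-480 (Step 2) | > 450 at any time | > 450 post-baseline | Newly > 450 |
|---|---|---|---|---|
| 410, 15 | 0.4% | 2.1% | 1.8% | 1.6% |
| 410, 20 | 2.3% | 7.2% | 6.5% | 4.8% |
| 410, 25 | 5.2% | 12.4% | 11.7% | 7.0% |
| 420, 15 | 2.3% | 9.7% | 8.7% | 7.3% |
| 420, 20 | 6.6% | 17.4% | 16.3% | 10.7% |
| 420, 25 | 10.8% | 22.6% | 21.4% | 11.5% |
| 430, 15 | 9.1% | 28.2% | 26.1% | 19.1% |
| 430, 20 | 15.3% | 33.9% | 32.1% | 18.0% |
| 430, 25 | 19.4% | 36.1% | 34.7% | 16.3% |

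Two things follow.

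- Restricting to post-baseline ECGs removes little (17.4% to 16.3% in the middle setting). The baseline condition does most of the work (16.3% to 10.7%).
- Of those counted post-baseline, the fraction already above 450 ms at baseline is (post-baseline − newly)/post-baseline. It runs from about 11% (410, 15: 0.2/1.8) to 53% (430, 25: 18.4/34.7). In eight of the nine settings most of the counted cases cross the limit through within-person variation over repeated ECGs, and a newly-occurring count still contains them.

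**The case against.** The case for leaving the plan alone has real substance.

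- **Labelling.** A reader might infer that the SAP reports baseline values as on-drug prolongation. It does not. It calls them outliers and nowhere describes them as treatment-emergent or drug-related. This stands.
- **Other outputs.** The > 30 ms category is not triggered by a stable high baseline, nor is the alert rule. Changes are summarized by visit, ECG values are listed, and clinically significant ECG abnormalities are reported as adverse events, whose analysis is limited to new or worsening ones. So the plan does use each participant's baseline elsewhere. This stands, but none of these outputs is crossed with the > 450 ms count, so that count remains unsorted.
- **Unseen shells.** Shells for non-standard tables are in a separate document and might restrict Table 3.5.6 to post-baseline ECGs. That cannot be excluded, but by Step 3 such a restriction alone changes little.
- **The > 500 ms line.** A reader might infer that both absolute limits are equally affected. They are not: a participant stable at an eligible QTcF of 480 ms or less does not reach 500 ms on that measure. The line is affected only if someone enters above 500 ms.
- **Size.** A reader might take the no-effect percentages as the amount by which the table overstates a QT signal. They rest on assumed distributions and mostly reflect within-person variation, so they do not support that.
- **Entry above 480 ms.** A reader might treat this as settled. It rests on Protocol 8.3.4, which conflicts with criterion 14 and with Section 5. The point here does not need it.

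**Conclusion.** The point holds in a limited form. By the documents' own limits, a participant eligible at 451 to 480 ms is counted in the > 450 ms category without any change. No planned ECG table separates such cases from new ones, although the SAP makes that separation for laboratory grades.

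The number of participants involved is unknown. It is about 1 to 33 of 170 (0.4% to 19.4%) if QTc is normal with mean 410 to 430 ms and SD 15 to 25 ms, cut at 480 ms. The consequence is an ambiguous descriptive count that can only err towards including too many. It is not a mislabelled drug effect, and the primary analysis is not affected. Because the remedy is cheap and uses data already collected, it is worth making.

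**What to change.** In SAP 8.5 and Table 3.5.6:

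1. Base the absolute QT/QTc categories on post-baseline ECGs, and say so.
2. Report newly occurring cases for each limit: baseline at or below it, worst post-baseline value above it. Use the averaged pre-dose baseline that SAP 8.5 already defines.
3. Add a table of baseline category by worst post-baseline category, in the style of the laboratory shift tables. It also shows how many newly occurring cases are small crossings from just below a limit.
4. Keep the present count as a second line.

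The cost is a few sentences in the SAP and slightly more programming. No new data or visits are needed.

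Separately, the sponsor must reconcile Protocol 8.3.4 (entry after a single QTc above 480 ms, by averaging or by approval), criterion 14 and the ban on waivers in Section 5. Which entry rule applies is for the sponsor to decide, and the analysis change above does not depend on it.
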